2.2 Primary Objectives

Primary Objective	Endpoint(s)	Time Frame
1. Cohort A: To determine the feasibility of metastatic lesion detection in using ^{11}C -YJH08 PET.	Cohort A: Sensitivity of metastatic lesion detection in using ^{11}C -YJH08 PET.	2 days
2. Cohort B and C: To determine the mean percent change from baseline at the time of progression on systemic therapy in $\text{SUV}_{\text{max-ave}}$ on paired ^{11}C -YJH08 PET on a per-patient and per-lesion basis.	Cohort B and C: Mean percent change from baseline at the time of progression on systemic therapy in $\text{SUV}_{\text{max-ave}}$ on paired ^{11}C -YJH08 PET on a per-patient and per-lesion basis.	Baseline to time of progression

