7.1 Imaging Analysis

A trained nuclear medicine physician will evaluate the reconstructed PET, CT or MRI, and fused PET/CT or PET/MR images using a PET volume computer-assisted reading software package. A positive lesion on PET will be defined as a focus of activity with at least 1.5 times higher SUV compared with mediastinal blood pool that is not attributable to other etiologies of tracer distribution (e.g. inflammation, excretion). A volume of interest (VOI) will be semiautomatically placed around each lesion, and the calculated maximum standard uptake value (SUV_{max}) will be recorded for each lesion, including lesions that are detected on standard scans but are not positive on PET. Adjusted SUV_{max} data will then be averaged across all lesions within a given patient ($SUV_{max-avg}$). In order to avoid clustering effects, analysis will be limited to the five largest osseous metastases and all visceral/soft tissue metastases.

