7.2 Determination of Sample Size

A convenience sample size of approximately 6 patients for Cohort A is selected to collect sufficient scan data to ensure adequate organ dosimetry and determination of the optimal uptake time following administration of ^{11}C -YJH08. Additional patients may be accrued as necessary to optimize imaging acquisition parameters prior to proceeding to Cohort B and C enrollment.

Success for Cohort A will be defined as technically successful injection of radiotracer with expected biodistribution and visualization of radiotracer uptake in the expected location of a metastasis based on conventional imaging in at least one patient. If no metastases are visualized despite varying uptake time and injected dose after 6 or more patients are enrolled in Cohort A, then accrual will not proceed to Cohorts B and C.

For patients enrolled in Cohorts B and C, a convenience sample size of 10 evaluable patients per cohort is chosen to provide preliminary estimates of sensitivity of lesion detection on PET compared to conventional imaging. We expect 20% inevaluable rate over the course of the study; we will recruit 12 patients in each cohort to achieve the target sample size.

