7.7.2 Primary Analysis

For Cohort A, Using as a cut-off to define a positive lesion on PET as a lesion with SUV at least 1.5 times higher than mediastinal blood pool, the sensitivity of ^{11}C -YJH08 PET will be descriptively reported on a lesion-per-lesion basis, using as reference standard staging scans including CT or MRI of the chest/abdomen/pelvis.

For Cohorts B and C, the median percent change from baseline, and range of SUV_{max} (across all metastatic lesions per patient) and $\text{SUV}_{\text{max-ave}}$ (in each study cohort) will be descriptively reported using mediastinal blood pool and normal organ as background uptake values. Wilcoxon signed rank test will be used to compare the follow up to baseline PET scan values at lesion level and patient level.

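### If Section 7.1's cap on bone lesions applies to Cohort A's sensitivity, the bone component is selected by size and may be overstated in patients with more than five bone metastases

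*Combined protocol and SAP*

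**What the plan says.** Section 2.2 gives Cohort A's primary endpoint as "Sensitivity of metastatic lesion detection in using" the tracer. Section 7.7.2 says how it is reported: "PET will be descriptively reported on a lesion-per-lesion basis, using as reference standard staging scans including CT or MRI of the chest/abdomen/pelvis". No sensitivity by site or by lesion size is planned; Section 7.7.3 describes only SUVmax by site of disease.

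Section 7.1 defines a positive lesion as "a focus of activity with at least 1.5 times higher SUV compared with mediastinal blood pool", with no size criterion. SUVmax is recorded for each lesion, "including lesions that are detected on standard scans but are not positive on PET". After describing how SUVmax is averaged within a patient, it adds: "In order to avoid clustering effects, analysis will be limited to the five largest osseous metastases", plus all visceral and soft tissue lesions. Clustering is the only reason given. The text does not say how largest is measured. That the limit is per patient is implied by the preceding sentence but not stated.

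**The concern.** The cap is worded for analysis in general and sits in the section that also defines PET positivity. On its natural reading it therefore sets the denominator of the primary sensitivity as well as the lesions entering SUVmax-ave.

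For an average of uptake, a limit on lesions per patient is a convention. For sensitivity, the choice of lesions decides what is being estimated. Positivity is a fixed multiple of blood pool, and a small lesion is less likely to reach it if PET blurring lowers its apparent uptake. That is general imaging reasoning; the documents do not state it for this tracer. Dropping the smaller bone lesions would then remove the likeliest misses, while soft tissue lesions of every size stay in. The result would be a mixture of sensitivity for each patient's largest bone lesions and sensitivity for all soft tissue lesions, reported as sensitivity of metastatic lesion detection.

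The issue reaches past Cohort A. Section 7.2 gives preliminary estimates of sensitivity as the reason for 10 evaluable patients in each of Cohorts B and C, and Section 2.1 makes high sensitivity their hypothesis. The same cap would carry into those estimates, and Cohort B consists of metastatic CRPC patients, some of whom may have many bone lesions.

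**Working it through.** **Is there a plan figure to reproduce?** No. Section 7.2 says "A convenience sample size of approximately 6 patients for Cohort A is selected to collect sufficient scan data". It gives no target sensitivity, expected lesion count or precision, so every input below except the cap of five is an assumption.

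**Bone component.** Let a patient have M bone lesions, with sensitivity pL in the five largest and pS in the rest.

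- Capped bone sensitivity (M > 5): pL
- All-lesion bone sensitivity: [5·pL + (M − 5)·pS] / M
- Difference: (pL − pS)·(M − 5)/M for M > 5, and 0 for M ≤ 5

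The multiplier (M − 5)/M is 0.50 at M = 10 and 0.75 at M = 20. Capped minus all-lesion bone sensitivity, in points:

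| pL | pS | M ≤ 5 | M = 10 | M = 20 |
|---|---|---|---|---|
| 0.90 | 0.90 | 0 | 0 | 0 |
| 0.90 | 0.80 | 0 | 5 | 7.5 |
| 0.90 | 0.70 | 0 | 10 | 15 |
| 0.90 | 0.50 | 0 | 20 | 30 |
| 0.70 | 0.90 | 0 | −10 | −15 |

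The last row shows that the sign depends on detection rising with size.

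**Smooth size effect.** As a check without two fixed classes, lesion size was simulated as standard normal, with detection probability logistic(1 + slope × size in SD), over 20,000 simulated patients per setting. The excess in bone sensitivity was:

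| Slope | M = 4 | M = 8 | M = 15 | M = 30 |
|---|---|---|---|---|
| 0 | 0 | 0 | 0 | 0 |
| 1 | 0 | 10.5 | 17.4 | 21.6 |
| 2 | 0 | 17.7 | 28.2 | 32.3 |

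**Pooled sensitivity.** This is the figure Section 7.7.2 reports. Add V visceral/soft tissue lesions with sensitivity pV.

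- Capped: (5·pL + V·pV) / (5 + V)
- All lesions: [5·pL + (M − 5)·pS + V·pV] / (M + V)

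With pL = 0.90, pS = 0.70, M = 20 and V = 5, these become (4.5 + 5·pV)/10 and (15 + 5·pV)/25:

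| pV | Capped | All lesions | Difference (points) |
|---|---|---|---|
| 0.90 | 0.90 | 0.78 | +12 |
| 0.60 | 0.75 | 0.72 | +3 |
| 0.30 | 0.60 | 0.66 | −6 |

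Dropping lesions raises the pooled figure only if the dropped ones are detected less often than the average of those kept. Here the sign changes where (4.5 + 5·pV)/10 = 0.70, that is at pV = 0.50.

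**Does the cap deal with clustering?** Only in part. Up to five bone lesions and an unlimited number of soft tissue lesions still come from the same patient. Choosing the retained lesions by size adds nothing to the control of clustering.

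**The case against.** The scope can be disputed. The cap follows directly after the sentence on averaging SUVmax, where limiting one patient's many bone lesions makes sense, and Section 7.7.2 restates the positivity threshold and reference standard without the cap. The narrower reading is therefore possible. It does not remove the point: the text leaves the primary endpoint's denominator open, and one sentence would settle it.

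The consequences are limited, and this stands. Cohort A takes any metastatic solid tumor, does not require bone disease, and has about six patients. Sensitivity is reported descriptively, with no test or threshold. Under Section 7.2 the go-ahead needs uptake at a known metastasis in at least one patient, which the cap would not plausibly change. SUVmax is recorded for each lesion, so an all-lesion figure could be computed later. The documents do not say, though, that it will be.

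Three stronger readings are tempting and are not supported:

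- A reader might infer that Cohort A's primary sensitivity is overstated. The reported figure pools all sites, and its shift can take either sign.
- A reader might infer that a planned comparison of bone with soft tissue is spoiled. No sensitivity by site is planned.
- A reader might infer that the retained bone lesions are known to be the ones PET sees best. The documents say nothing on how detection with this tracer depends on lesion size.

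**Conclusion.** The point holds conditionally. If the cap governs sensitivity, which is the natural but not the only reading, the bone component rests on a size-selected set of lesions. It may then be overstated in patients with more than five bone metastases, provided detection rises with lesion size. There is no effect at five or fewer. The pooled primary figure is distorted in a direction set largely by soft tissue sensitivity: +12 to −6 points in the worked example.

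The size of the effect cannot be derived from the documents. The range of about 5 to 30 points for bone at 10 to 20 lesions rests on assumed values of 0.90 in the five largest lesions and 0.80 to 0.50 in the rest. The matter concerns what the sensitivity figure means in Cohort A, and later in Cohorts B and C; the decision to proceed does not turn on it. The change is worth making mainly because it is cheap and size selection is not needed to handle clustering.

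**What to change.** In Sections 7.1 and 7.7.2:

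- State that the limit of five osseous lesions per patient applies only to the SUVmax-ave calculation.
- Compute sensitivity on every lesion identified on the staging scans, and report it overall and separately for bone and visceral/soft tissue. Apply the same rule to any sensitivity estimate in Cohorts B and C.
- Handle clustering by listing each patient's detected and total lesions with a patient-level summary, or by a cluster-adjusted interval. With about six patients such an interval will be rough, so the patient-level display should be shown in any case.

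Tables by lesion size class are optional; with about six patients most cells would be sparse.

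The cost is revised wording and some extra lesion matching on images already acquired, with no new scans or patients. The reported sensitivity may come out lower. Patients with many bone lesions will also weigh more in the overall lesion-level figure, which is why the patient-level summary should accompany it.

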7.2 Determination of Sample Size

A convenience sample size of approximately 6 patients for Cohort A is selected to collect sufficient scan data to ensure adequate organ dosimetry and determination of the optimal uptake time following administration of ^{11}C -YJH08. Additional patients may be accrued as necessary to optimize imaging acquisition parameters prior to proceeding to Cohort B and C enrollment.

Success for Cohort A will be defined as technically successful injection of radiotracer with expected biodistribution and visualization of radiotracer uptake in the expected location of a metastasis based on conventional imaging in at least one patient. If no metastases are visualized despite varying uptake time and injected dose after 6 or more patients are enrolled in Cohort A, then accrual will not proceed to Cohorts B and C.

For patients enrolled in Cohorts B and C, a convenience sample size of 10 evaluable patients per cohort is chosen to provide preliminary estimates of sensitivity of lesion detection on PET compared to conventional imaging. We expect 20% inevaluable rate over the course of the study; we will recruit 12 patients in each cohort to achieve the target sample size.

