2.1 Study Hypotheses

1. **Cohort A:** ^{11}C -YJH08 PET will demonstrate feasibility of uptake within one or more metastatic lesions.
2. **Cohort B and C:** ^{11}C -YJH08 PET will detect metastatic lesions with high sensitivity using conventional imaging as a reference standard.

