7.7.3 Analysis of Secondary and Exploratory Endpoints

The frequency and severity of adverse events following ^{11}C -YJH08 injection will be descriptively reported, using CTCAE v 5.0. Organ dosimetry on PET will be calculated using standard technique.

The median and range for intra-tumoral SUV_{max} within metastatic lesions will be descriptively reported to asses for intra-tumoral heterogeneity and differences in uptake by site of disease.

For the purposes of analyzing the association between baseline and percent change from baseline in $\text{SUV}_{\text{max-ave}}$ with subsequent clinical outcomes, the cohort will be dichotomized above and below the median for the study cohort. The PSA response rate (PCWG3 criteria; Cohort B only), clinical benefit rate, and objective response rate (in subset of measurable tumors by RECIST 1.1) will be compared between dichotomized groups using the chi-squared test. The

log rank test will be used to compare progression-free survival between dichotomized subgroups.

For patients who undergo optional tumor biopsy with evaluable tumor content, the correlation between SUV_{max} of the target lesion on PET with GR expression by IHC (using H-score method) will be computed using Pearson correlation method. Likewise, the correlation between SUV_{max} on PET with GR transcriptional signature activity by RNA-seq will be determined using Pearson correlation method when sufficient tumor content permits transcriptional analysis.

No adjustment will be made for multiple comparisons for the analysis of the secondary and exploratory endpoints.

8 Study Management

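### Cohorts B and C: the hypothesis and sample size concern lesion-detection sensitivity, but no endpoint or analysis estimates it there, and the one primary endpoint rests on an optional scan

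*Combined protocol and SAP*

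**What the plan says.** On the question for Cohorts B and C, section 2.1 states that "PET will detect metastatic lesions with high sensitivity using conventional imaging as a reference standard". Section 7.2 gives the reason for the size: "a convenience sample size of 10 evaluable patients per cohort is chosen to provide preliminary estimates of sensitivity of lesion detection on PET". It then allows for 20% inevaluable and recruits 12 per cohort.

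On endpoints, section 2.2 gives Cohort A "Sensitivity of metastatic lesion detection in using" the tracer PET. It gives Cohorts B and C the "mean percent change from baseline at the time of progression on systemic therapy in" SUVmax-ave on paired scans. No other B/C primary endpoint is listed.

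On analysis, section 7.7.2 says for Cohort A that the sensitivity of "PET will be descriptively reported on a lesion-per-lesion basis, using as reference standard staging scans including CT or MRI of the chest/abdomen/pelvis". For the other two cohorts it says: "For Cohorts B and C, the median percent change from baseline, and range of" SUVmax and SUVmax-ave, with a Wilcoxon signed rank test at lesion and patient level. Section 7.7.3 adds that the median and range of SUVmax "within metastatic lesions will be descriptively reported to asses for intra-tumoral heterogeneity and differences in uptake by site of disease".

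On the data, section 7.1 records SUVmax for every lesion, "including lesions that are detected on standard scans but are not positive on PET", without limiting this to one cohort. Section 5.2.3 makes the progression scan optional. Section 7.4 does not list a missing second scan as a reason for replacement, and 7.7.1 does not impute missing values.

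**The concern.** Hypothesis, sample-size basis, primary endpoint and analysis should describe one question. For Cohorts B and C, 20 of the roughly 26 planned patients, they describe two. The first, sensitivity, has a hypothesis and a sample-size rationale but no endpoint and no analysis. The second, paired SUV change, has an endpoint and an analysis but no hypothesis and no sample-size rationale.

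Two things are at stake. The B/C hypothesis would go unanswered in the planned report, and the number 10 would be justified by a quantity that nothing estimates. If sensitivity were added after the scans had been read, its status as primary or secondary, the form of its interval and the meaning of high would be settled with the data in view.

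The endpoint that is planned exists only for patients who progress and accept a second scan. Non-progressors fall outside its definition. Progressors without a second scan are missing data, and the plan does not ask for their number.

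**Working it through.** **1. The sections side by side (Cohorts B and C)**

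| Element | Section | Sensitivity | Paired SUV change |
|---|---|---|---|
| Hypothesis | 2.1 | yes | no |
| Sample-size basis | 7.2 | yes | no |
| Primary endpoint | 2.2 | no (Cohort A only) | yes |
| Secondary or exploratory endpoint | 2.3, 2.4 | no | no |
| Primary analysis | 7.7.2 | no (Cohort A only) | yes |
| Other analysis | 7.7.3 | no | only as a predictor of clinical outcome |

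The uptake summaries in 2.3 and 7.7.3 (SUVmax by site, tumor-to-background signal) do not fill the gap. None of them is the proportion of reference lesions that PET detects.

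**2. The plan's own recruitment figure**

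Inputs from 7.2: 10 evaluable, 20% loss, 12 recruited.
- 10 × 1.2 = 12, which reproduces the stated figure.
- 10 / 0.8 = 12.5, rounded up to 13, one more than stated.
- Without replacement, 12 × 0.8 = 9.6 expected evaluable, and P(at least 10 of 12) = 0.558 by the binomial.
- Totals: 6 + 10 + 10 = 26 (section 3.2); 6 + 12 + 12 = 30 (if 7.2 is followed).

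**3. Precision of a B/C sensitivity estimate**

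The document gives no expected sensitivity, lesion count or within-patient correlation. Assumed: sensitivity 0.8, K = 10 patients, m = 3 or 8 reference lesions each, correlation r = 0.2 or 0.4.

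Effective lesions: n_eff = K·m / (1 + (m − 1)·r). Half-width = c × √(0.8 × 0.2 / n_eff), with c = 1.96 (normal) or 2.262 (t on 9 df).

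| m | r | n_eff | Normal | t, 9 df |
|---|---|---|---|---|
| 3 | 0.2 | 30/1.4 = 21.4 | 0.169 | 0.195 |
| 3 | 0.4 | 30/1.8 = 16.7 | 0.192 | 0.222 |
| 8 | 0.2 | 80/2.4 = 33.3 | 0.136 | 0.157 |
| 8 | 0.4 | 80/3.8 = 21.1 | 0.171 | 0.197 |

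This gives 14 to 22 percentage points either side. Ignoring clustering (r = 0) gives 0.143 for m = 3 and 0.088 for m = 8, which is too narrow.

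In a beta-binomial simulation (10 patients; m = 3, 5, 8; r = 0.2, 0.4; 4000 runs), nominal 95% exact intervals that ignored clustering covered the truth 72% to 95% of the time. A bootstrap resampling patients (1000 resamples) covered it 88% to 92% of the time. That is more even, but still slightly short with so few patients.

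**4. Number of pairs**

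The document gives no uptake of the second scan. Let u be the assumed share of recruits who progress and have it. Expected pairs per cohort are 12u: 3.6 (u = 0.3), 6.0 (0.5), 8.4 (0.7), 10.8 (0.9). If the 20% loss is separate, multiply by 0.8: 2.9, 4.8, 6.7, 8.6. These figures are illustrative only.

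**The case against.** The strongest reply is that this is a first-in-human phase 1 study with an openly declared convenience sample and no power claim, and that sensitivity in B and C can be computed anyway. Much of this stands. Section 7.1 already fixes both the lesion set (up to five osseous lesions, chosen by size, plus every visceral or soft-tissue lesion) and the positivity rule (1.5 times mediastinal blood pool) for all cohorts. A reader might infer that the investigators would be free to choose lesions afterwards; the document does not support that. What remains open is whether sensitivity is a B/C endpoint at all, its status, its interval and the meaning of high.

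A second reply is that 10 evaluable could mean 10 complete pairs, since the 20% loss is said to run over the whole study and evaluable is not defined. This is possible but weaker. The sentence in 7.2 ties the 10 to sensitivity, which needs only the baseline scan, and neither replacement reason in 7.4 covers a missing second scan.

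A reader might also infer from the 9.6 that recruiting 12 is an error. The document does not support that either. Section 7.4 lets patients be replaced for a failed baseline scan or poor scan timing, so 9.6 and the 56% chance of reaching 10 are no-replacement figures. The stated 12 is within one patient of the usual calculation.

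**Conclusion.** The mismatch is in the text and rests on no assumption: the B/C hypothesis and sample-size rationale concern a quantity that no B/C endpoint or analysis estimates. It should be settled before the B/C scans are analysed.

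The planned primary endpoint does not replace the missing one. It depends on an optional scan, was not the basis for the 10 patients, and has no expected number of pairs. It would be too strong to say that the paired analysis must fail, because the number of pairs depends on an uptake that the document does not give.

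Nor does the point require more patients. A convenience sample is acceptable for preliminary estimates, provided that the estimates are planned. The 14 to 22 point half-width shows what such an estimate could deliver under the stated assumptions; it is not a reason to reject the size.

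**What to change.** 1. List baseline per-lesion sensitivity as a B/C endpoint in 2.2 or 2.3, with its status stated, and add it to 7.7.2 or 7.7.3. Use the 7.1 positivity rule and the staging CT/MRI reference standard already named for Cohort A. Report it as estimation, with an interval that allows for lesions clustering within patients, such as a bootstrap that resamples patients, and note that with about 10 patients it will be somewhat too narrow. Give the number of osseous lesions left out by the five-lesion limit, since keeping the largest may favour easily detected lesions. Alternatively, if the sponsor intends paired SUV change as the only B/C question, revise 2.1 and 7.2 to match it. Which was meant is the sponsor's decision.
2. In either case, state that the paired result applies to patients who progressed and had the second scan. Report the number of pairs and the number of progressors without a second scan.
3. Minor: use one summary, mean or median, in 2.2 and 7.7.2, and reconcile about 26 enrolled (3.2) with 12 recruited per cohort (7.2), which makes 30 in all. Do not write 9.6 in as the yield.

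The cost is wording in these sections and, under the first option, one analysis of lesion data already recorded under 7.1. No patients or scans are added beyond those in 7.2. The downside is that the sensitivity intervals will be wide, and the osseous limit must be stated as a limitation.
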